## List of Abbreviations

ABI	Ankle-Brachial Index
ACS	Acute Coronary Syndrome
AE	Adverse Event
ANOVA	Analysis of Variance
B/P	Blood Pressure
BUN	Blood Urea Nitrogen
CFR	Code of Federal Regulations
CKD	Chronic Kidney Disease
CLI	Critical Limb Ischemia
COPD	Chronic Obstructive Pulmonary Disease
Crt	Creatinine
CVA	Cerebrovascular Accident
DAPT	Dual Antiplatelet Therapy
DM	Data Management
eCRF	Electronic Case Report Form
ESC	Executive Steering Committee
FDA	Food and Drug Administration
HbA1c	Hemoglobin A1c
Hct	Hematocrit
HDL	High-Density Lipoprotein
Hgb	Hemoglobin
HR	Heart Rate
INR	International Normalized Ratio
IRB	Institutional Review Board
ISS	Investigator Sponsored Study
LDL	Low-Density Lipoprotein
LS	Least Squares
mg	milligrams
mmHg	Millimeters Mercury
MMRM	Mixed Model Repeated Measures
PAD	Peripheral Arterial Disease
Plt	Platelet Count
PTA	Percutaneous Transluminal Angioplasty
PTT	Partial Thromboplastin Time
REDCap	Research Electronic Data Capture
SAE	Serious Adverse Event

SAS	Statistical Analysis System
SD	Standard Deviation
SOC	Standard of Care
SPSS	Statistical Package for the Social Sciences
SSL	Secure Sockets Layer
SPP	Skin Perfusion Pressure
TBI	Toe-Brachial Index
Tchol	Total Cholesterol
TcPO2	Transcutaneous Oxygen Concentration
Tg	Triglycerides
TIA	Transient Ischemic Attack
TSP	Toe-Systolic Pressure
ULN	Upper Limit of Normal

## Study Synopsis

Title	Establishing the microcirculatory effects of ticagrelor on tissue perfusion in critical limb ischemia
Sponsor	[name]
Rationale	Ticagrelor has emerged as a novel P2Y12 adenosine receptor antagonist studied primarily in the treatment of coronary heart disease, but with properties that make the drug suitable for study in PAD. Beyond its antiplatelet effects, ticagrelor's ability to inhibit uptake of adenosine may provide cytoprotective and reparative properties that could prove therapeutic to patients with advanced PAD. Indeed, oral administration of ticagrelor to animals prevents contraction of vascular smooth muscle: an effect not seen with clopidogrel or prasugrel (5). Similar to effects seen with clopidogrel, ticagrelor may reduce leukocyte-platelet adhesion and improve microcirculatory function during ischemia by reducing blood viscosity (6). In addition to these beneficial antiplatelet effects, ticagrelor may provide additional benefit in smooth muscle relaxation by promoting serum adenosine concentrations.
Study Center	Cleveland Clinic and University Hospital in Cleveland
Indication	Rutherford Classification Stage IV through VI PAD
Study Objectives	
The primary goal of the proposed research is to determine if ticagrelor can induce a clinically significant change in transcutaneous oxygen concentration (TcPO2) superior to that induced by clopidogrel, among advanced cases of recently revascularized peripheral arterial disease (PAD).
 
Secondary objectives include:
 
 
1) to compare the rate of wound healing at 6 months between treatment groups among Rutherford Classification Stage V-VI patients
 
2) to determine if other markers of blood flow improve with treatment with ticagrelor.
 

Study Design	
This is a 2-arm randomized, active-controlled, pilot study. Patients over the age of 18 presenting with Rutherford Classification Stage IV-VI PAD will be included. Sixty (N=60) eligible patients who have given their consent to participate will be randomized to one of the following treatments:
 
 
• Clopidogrel (75 mg by mouth daily)
 
• Ticagrelor (90 mg by mouth twice daily)
 
 
All patients will be followed for 6 months after enrollment, with the primary endpoint assessed at 6 months after randomization.

Number of Patients	A sample size of 60 patients (30 per group) provides 90% power to detect an 8±8 mmHg difference in TcPO 2 between groups.

Target Population	Patients with critical limb ischemia either Rutherford Stage IV (without wounds) or Stage V-VI (with concomitant vascular insufficiency wounds) that have been recently revascularized.
Duration of patient participation and duration of the study	The total duration of the study is expected to be 54 months including 48 months for patient recruitment and 6 months for final patient follow-up. Patients will participate in the study for approximately 6 months.
Key Selection Criteria	
INCLUSION CRITERIA
 
 
• Adults age 18-100 years with Rutherford Classification Stage IV through VI PAD with a percutaneous lower extremity arterial angiography with arterial intervention in the past 2 weeks
 
• Willingness to sign informed consent
 
• Ability to return for follow-up visits
 
• A female patient of childbearing potential who is sexually active must agree to use adequate contraception from screening until 30 days after receiving the last dose of study drug.
 
 
EXCLUSION CRITERIA
 
 
• Intolerance to thienopyridines
 
• Hypersensitivity to ticagrelor or any component of the product
 
• Concomitant use of oral anticoagulation with vitamin K antagonist, factor Xa inhibitor, or direct thrombin inhibitor
 
• History of intracranial hemorrhage
 
• History of severe hepatic impairment defined by baseline transaminase greater than or equal to 3x ULN or any elevation in bilirubin
 
• Active bleeding
 
• Allergy to aspirin
 
• Baseline TcPO2 < 10 mmHg post angiography
 
• Resting pre-procedure heart rate < 50 beats-per-minute without a permanent pacemaker and not on an atrioventricular nodal blocking agent
 
• Severe COPD on home oxygen therapy
 
• Patients on strong CYP3A inhibitors and/or CYP3A inducers that cannot be stopped for the course of the study.
 

Study Visit Schedule and Assessments	Visits will occur at screening (baseline) post angiography, and at 3 and 6 months.
Test Product, Dose, and Mode of Administration	Patients will be randomized to either ticagrelor 90 mg by mouth twice daily or clopidogrel 75 mg by mouth daily.
Concomitant Medications	Aspirin 81 mg by mouth every day

Prohibited Medications	
 
• Concomitant use of oral anticoagulation with a vitamin K antagonist, factor Xa inhibitor, or direct thrombin inhibitor
 
• Aspirin > 100mg per day
 

Endpoints	
Primary endpoint
 
 
• Absolute change in TcPO2 from baseline to 6 months
 
 
Secondary endpoints
 
 
• Rate of wound healing from baseline to month 6 in treatment groups for patients with Rutherford Stage V-VI PAD
 
• Change in ankle-brachial index (ABI), toe-brachial index (TBI), toe-systolic pressure (TSP) and skin perfusion pressure (SPP) from baseline to month 6 in treatment groups
 
• Major adverse limb events including a composite of surgical limb loss or any major vascular repeat revascularization, including thrombectomy, thrombolysis, or major lower-extremity surgical procedure from baseline to month 6 in treatment groups
 
• Percent change in TcPO2 from baseline to 6 months
 
• Percent change and absolute change in TcPO2 from baseline to month 3
 

AE/ SAE Collection	
AEs
 
 
• Self-reported shortness of breath with symptomatic bradycardia
 
• Events that are not listed in the current labeling for the drugs
 
• Events that lead to discontinuation of drug or result in a dose modification
 
 
SAEs
 
 
• Death.
 
• Life threatening AEs.
 
• Requires inpatient hospitalization or prolongation of existing hospitalization.
 
• A disability/incapacity.
 
• A congenital anomaly/birth defect in the offspring of a patient who received drug.
 
• Important medical event that may jeopardize the subject or may require medical intervention to prevent one of the outcomes listed above.
 
 
Other SAEs of Special Interest
 
 
• Major bleeding defined as a composite of fatal bleeding, intracranial bleeding, hypovolemic shock or severe hypotension due to bleeding requiring pressors, or need for transfusion of at least 2 units in any 24-hour period.
 
• Major adverse limb events (surgical limb loss, major repeat revascularizations including thrombectomy, thrombolysis, or major lower extremity surgical procedure.
 

Safety Evaluations	Safety endpoints to be assessed include major bleeding, self-reported dyspnea and reported symptomatic bradycardia.
Statistical Methodology	
Analysis of the Primary and Secondary Endpoints
 
Baseline covariates will be compared with Fisher’s exact test for categorical variables and two-sample t-test for continuous variables with a normal distribution or rank sum test if non-normally distributed between treatment groups. All comparisons between treatment groups will be performed as intent-to-treat using two-tailed significance testing at a value of 0.05.
 
Mixed model repeated measures analysis (MMRM) will be used to conduct the between-group comparison of absolute change in TcPO2 at 3 months and 6 months follow-up, with adjustment of baseline TcPO2 level following revascularization. Estimated within-group least squares (LS) means of TcPO2 and between-group differences of LS means in TcPO2 at 3- and at 6-month follow-up time points will be obtained from the MMRM modeling.
 
If the TcPO2 data is not normally distributed, the same MMRM method will be performed to analyze the rank transformed TcPO2 data, however the descriptive data is presented with median (interquartile range), and the between-group differences are shown using F statistics. Meanwhile, relevant nonparametric methods will be applied as sensitivity analysis. Friedman test will be conducted to compare the TcPO2 repeated measures from baseline to 6 months follow-up between the treatment groups. A Wilcoxon signed rank test will be used to assess intragroup change in TcPO2 at 3- and at 6-month follow-up.
 
The absolute change in TcPO2 over time and other continuous secondary endpoints will be analyzed using the same strategies. Safety endpoints, adverse events and other categorical secondary endpoints will be analyzed using Fisher’s exact test. The relationships between the primary endpoint of change in TcPO2 at 6 months follow-up and the continuous secondary endpoints will be explored by regression analysis.

## Study Visits

Study Procedures	Screening/ Baseline	3 Months (+/- 1 week)	6 Months (+/- 1 week)
Informed Consent	X		
Demographics	X		
Medical History	X		
Rutherford Classification	X	X	X
ABI, TBI, TSP	X	X	X
Wound Size	X	X	X
Vital Signs	X	X	X
Record Baseline Labs 	X		
Urine Pregnancy Test 	X		
Angiographic Data	X		
TcPO2 measurement	X 	X	X
SPP measurement	X	X	X
Concomitant Medications	X	X	X
Randomization	X		
Dispense Study Drug	X	X	
Assessment of wound healing		X	X
Study medication compliance		X	X
Collect AEs & SAEs		X	X

Baseline labs will be obtained from local labs performed in the month prior to screening and include the following: Blood urea nitrogen, creatinine, HbA1c, hemoglobin, hematocrit, platelet count, international normalized ratio, partial thromboplastin time, total cholesterol, low-density lipoprotein, high-density lipoprotein, triglycerides

For females of childbearing potential

Post angiography

## **1 Introduction**

### **1.1 Background**

Treatment of critical limb ischemia (CLI), an advanced form of peripheral arterial disease (PAD), has lagged behind other forms of cardiovascular disease. Lacking are novel medical strategies that promote ambulatory ability and, when CLI-related wounds are present, reconstitution of tissue oxygenation and tissue healing. Wound healing remains a distinct challenge, characterized by a complex interplay of neuropathic and microvascular circulatory deficiencies that promote inflammation and tissue hypoxia (1). Recent interest has focused on the role of adenosine, a ubiquitous purine nucleoside, and its reparative biological effects through neuromodulation and wound healing via A2A and A2B cellular receptors (2,3). Herein, we propose a first-in-man pilot study among patients revascularized for advanced symptomatic PAD, including patients with CLI-related vascular insufficiency wounds. Ticagrelor will be compared to clopidogrel, the post-angioplasty standard-of-care thienopyridine, in an evaluation of interval improvement in tissue oxygenation as assessed by tissue partial pressure of oxygen (TcPO2).

### **1.2 Rationale for use of ticagrelor**

Ticagrelor has emerged as a novel P2Y12 adenosine receptor antagonist studied primarily in the treatment of coronary heart disease, but with properties that make the drug suitable for study in PAD. Beyond its antiplatelet effects, ticagrelor's ability to inhibit uptake of adenosine may provide cytoprotective and reparative properties that could prove therapeutic to patients with advanced PAD. These beneficial properties may explain the striking reduction of adverse vascular outcomes observed in the PLATO Study and may represent a fundamental pharmacologic difference between ticagrelor – a carbocyclic nucleoside – and the thienopyridines (4). Indeed, oral administration of ticagrelor to animals prevents contraction of vascular smooth muscle: an effect not seen with clopidogrel or prasugrel (5). Similar to effects seen with clopidogrel, ticagrelor may reduce leukocyte-platelet adhesion and improve microcirculatory function during ischemia by reducing blood viscosity (6). In addition to these beneficial antiplatelet effects, ticagrelor may provide additional benefit in smooth muscle relaxation by promoting serum adenosine concentrations. In addition to its vasodilatory properties, adenosine has been shown to limit ischemia-related tissue injury. The addition of adenosine to thrombolytic therapy in acute myocardial infarction in 3 large randomized studies has demonstrated dramatic reduction in infarct size (7-9). To this end, a randomized, double-blind, phase IIIb multicenter study is underway comparing cardiovascular outcomes among an anticipated 11,500 patients with established PAD in the Examining Use of ticagrelor In PAD (EUCLID) Study (clinicaltrials.gov Identifier: NCT01732822). While this large clinical outcomes study is timely and highly important, a study demonstrating ticagrelor's microvascular effects is warranted. Ticagrelor's potentially beneficial pharmacologic properties may offer advantages of increased tissue oxygenation that promote wound healing and improve ambulatory ability in advanced PAD.

Similar to the endovascular treatment of coronary artery disease, percutaneous transluminal angioplasty (PTA) for PAD requires the use of dual-antiplatelet therapy (DAPT) to prevent thrombotic complications related to stent placement or balloon angioplasty. In a head-to-head comparison with clopidogrel among patients with acute coronary syndromes, ticagrelor has already shown impressive reductions in mortality without increasing the overall risk of major

bleeding (13). For patients undergoing PTA, DAPT is recommended for at least 30 days following the PTA procedure. The benefits of DAPT beyond 30-days after peripheral arterial intervention have been recently demonstrated; clopidogrel plus aspirin was superior to aspirin monotherapy for up to 6 months after PTA by preventing peri-procedural platelet activation and improved functional outcomes without increasing the risk of bleeding complications (14). Furthermore, even though costs associated with long-term DAPT are higher, clopidogrel has proven cost-effective over aspirin monotherapy for secondary prevention for vascular events among patients with PAD (15,16). With an anticipated antiplatelet benefit as robust as that of clopidogrel, ticagrelor may also demonstrate cost-effectiveness.

### **1.3 Rationale for use of TcPO2 and SPP**

To assess the potential perfusion benefits of ticagrelor, baseline and follow-up assessment with TcPO2 will be used to compare relative effects of clopidogrel. TcPO2 requires cutaneous positioning of oximetry electrodes and has been validated as an appropriate clinical measure of tissue oxygenation in CLI (10). A distinct advantage of TcPO2 includes its ability to assess regional tissue oxygenation, such as at the external margins of a vascular insufficiency ulcer. TcPO2 also provides surrogate information of macro- and microvascular arterial perfusion with a prognostic signal; TcPO2 levels > 30 mmHg have been associated with higher rates of local wound healing (10,11).

Several noninvasive measures of local tissue perfusion provide complementary roles in management of patients with wounds related to tissue ischemia. Whereas ankle-brachial index (ABI) is a valid screening tool for PAD, advanced vascular calcification that often accompanies severe PAD also renders ABI less reliable, often by underestimating disease severity. Markers of microvascular perfusion, such as toe-brachial index, toe systolic pressure, TcPO2 and skin perfusion pressure have been suggested to be more accurate measures. TcPO2 may have improved accuracy in predicting wound healing relative to other modalities, including toe systolic pressure (TSP) (12). However, there exist no simultaneous comparisons of all four techniques among patients with advanced PAD. Therefore, an important feature of this study is to compare these techniques among patients with Rutherford Class IV-VI CLI.

Alternate noninvasive techniques to assess arterial flow in CLI have important limitations. Ankle-brachial index is the standard noninvasive test for PAD, although it can provide unreliable and overestimated results among those with advanced age, diabetes mellitus, and chronic kidney disease (10,11,17). Toe-blood pressure, including TBI and TSP, while prognostically useful in predicting wound healing, is not available among those with previous forefoot amputation. For these reasons, TcPO2 was selected for this study as a reliable assessment of regional tissue oxygenation, sensitive to improvements in microvascular perfusion. Similar to TcPO2, the utility of SPP has not been extensively characterized, although some studies suggest it is useful in assessing perivascular microcirculation of the wound (11). Distinct from the assessment of tissue oxygenation with TcPO2, SPP measures blood in the microcirculation around and within a wound. SPP is a painless test that measures microcirculatory blood flow using photoplethysmography with Doppler techniques. Therefore, SPP offers a complimentary and concurrent assessment of microcirculatory wound perfusion that may enhance understanding of healing in ischemic tissues.

## **2 Study Design**

## **2.1 Summary**

This is a prospective, randomized, unblinded, open-label, active controlled pilot study to evaluate the efficacy and safety of ticagrelor plus aspirin versus clopidogrel plus aspirin in patients with Rutherford Stage IV to VI PAD that have undergone a percutaneous transluminal angioplasty (PTA) of the lower extremities in the past 2 weeks.

This study will be conducted at the Cleveland Clinic and University Hospital in Cleveland, Ohio. A total of 60 patients are planned for this study.

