#### **4.2 Patient Enrollment and Randomization**

Enrollment will occur when a patient signs and dates an informed consent form and provides authorization to use protected health information.

A total of 60 patients will be randomized into 2 treatment groups in a 1:1 ratio (ticagrelor to clopidogrel). Permuted block randomization will be used to allocate patients to treatment groups. Fixed block sizes will be used to allocate treatment groups, thereby ensuring that sample size in each group is similar as the study progresses. Blocked randomization lists will be computer generated and blinded to the investigators. The investigator will not know the assigned treatment for a patient until the patient is randomization. Patients will not be blinded to their treatment group.

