##### **6.4.2 Measurement of TcPO2**

Assessment of TcPO2 will be performed using the Perimed Periflux System 5000 (Perimed Inc., Ardmore, PA) equipped with laser Doppler and transcutaneous oximetry function units. Before each measurement, the device will be calibrated as per manufacturer's specifications. Patients will be asked to refrain from tobacco use or caffeine 12 hours prior to TcPO2 assessment. All measurements will be performed in the supine position. A site distant from the diseased area (right subclavicular region) will be used as a reference value (12, 18).

Skin perfusion is strongly dependent upon skin temperature. Accurate and reproducible assessment of tissue oxygenation requires measurement at maximal hyperemia. Measurement at peak blood flow provides consistency of measurements at peak cutaneous blood flow reserve. Therefore, assessment of TcPO2 requires local tissue warming around the cutaneous ulcer site to

a prespecified temperature. As part of the Perimed system, the PF 5020 Temp Unit will be used to gradually warm the perimeter of the wound at sites of measurement to a steady state of 44°C (43-45°C) as per manufacturer specifications.

In patients with Stage IV (no wound) the level of the great toe will be used as the site for measurement of TcPO2. In the event of previous amputations, the most distal aspect of the foot will be used for the measurement. In order to ensure that subsequent assessments are consistent with the index measurement, the area used will be documented in the records

From room temperature (30-34°C), thermal steady state is achieved in 3-5 minutes and is maintained during tissue assessment. All subsequent TcPO2 assessments will be made at 44°C (43-45°C) to ensure maximal hyperemia and measurement accuracy. After the site of TcPO2 adhesion is prepared, the instrument is calibrated at thermal steady state (3-5 minutes). Continuous TcPO2 monitoring then commences over 10-15 minutes until transcutaneous oxygen pressure also reaches steady state.

Follow-up TcPO2 measurements (Perimed © Periflux System 5000) will be performed at 3 and 6 months after revascularization for the purposes of this study. Repeated measures for this study at 3 and 6 months are necessary to assess the interval change of TcPO2 and to provide additional accuracy of statistical modeling of secondary efficacy endpoints.

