## **11 Data Handling and Record Keeping**

### **11.1 Data Collection**

Data will be collected by the Nurse or Site Coordinator or designee. Data sources include patient reports and available medical records, including those from electronic medical record. Values for preoperative variables will be selected nearest to the date of the revascularization procedure, but used only if they were obtained within 30 days of the procedure.

C5Research Data Management will create a Case Report Form to document the agreed upon variables to be captured in the REDCap database.

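### No provision keeps whoever takes the month 3 and 6 TcPO2 readings, or assesses the wound, unaware of the treatment arm

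*Combined protocol and SAP*

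**What the plan says.** Section 2.1 calls the trial a "prospective, randomized, unblinded, open-label, active controlled pilot study". Section 4.2 adds: "Patients will not be blinded to their treatment group". The only masking is in the same section and concerns allocation: "Blocked randomization lists will be computer generated and blinded to the investigators", and "The investigator will not know the assigned treatment for a patient until the patient is randomization". It ends at randomization.

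The primary endpoint in the Synopsis is "Absolute change in TcPO2 from baseline to 6 months". Section 6.4.2 standardizes its measurement in several ways: calibration before each use, supine position, abstention from tobacco and caffeine, a subclavicular reference site, a target of 44°C with a 43-45°C range, and a record of the area used so that later visits match the first. For patients with wounds, the device is used to "gradually warm the perimeter of the wound at sites of measurement"; the number and position of those sites are not fixed. On timing, the section says: "Continuous TcPO 2 monitoring then commences over 10-15 minutes until transcutaneous oxygen pressure also reaches steady state". No numerical rule defines steady state.

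Sections 6.2 and 6.3 list wound size and healing at months 3 and 6 without a method, a healing criterion or an assessor. The same visits include the compliance check, adverse event collection and, at month 3, dispensing. On staffing, Section 11.1 says only: "Data will be collected by the Nurse or Site Coordinator or designee". Section 6.4 classes TcPO2 and SPP as study procedures, and wound assessment, ABI, TBI and TSP as standard of care.

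**The concern.** Giving the drugs openly does not require measuring the outcome openly. Section 9.2 states a hypothesis in favour of ticagrelor, and the primary comparison is a two-sided 0.05 test with a claimed 90% power. An operator who knows the arm and expects ticagrelor to do better could, without intending to, settle on a slightly different point of the wound edge or accept a plateau slightly earlier or later.

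The visit content makes knowledge of the arm likely unless it is prevented. Sections 5.3 and 7 describe the supplied study medication as ticagrelor, so dispensing it, or asking about compliance with it, reveals the arm. Nothing separates those tasks from the measurements.

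The wound endpoint, listed first among the secondary endpoints, is more exposed than TcPO2, because the plan says nothing about how healing is decided.

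**Working it through.** **1. The plan's own figures.** Section 9.2 gives a difference of 8 mmHg, SD 8, 90% power and two-sided 0.05.

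- n per group = 2 × (z₀.₉₇₅ + z₀.₉₀)² × (SD/difference)² = 2 × (1.960 + 1.2816)² × (8/8)² = 21.01, so 22 (23 with the exact t-test). The plan starts from 26, which these inputs do not reproduce.
- Its later steps roughly follow: 26/0.95 = 27.4, so 28; 28/0.925 = 30.3, against the plan's 30.
- At 30 per group the exact power on the stated inputs is 96.8%.

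The mismatch is on the conservative side. Masking changes neither sample size nor power, so the present point does not depend on it.

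**2. Is masking provided anywhere?** Section 4.2 conceals the list until assignment. Sections 6.2-6.4 (visits and measurements), 9 (statistics), 10 (committees) and 11 (data handling) name no masked operator, reader or adjudicator.

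**3. Can the analysis remove a shift?** Baseline TcPO2 is an eligibility criterion (Section 4.1.2) and is listed before randomization (Section 6.1), so it is taken to precede knowledge of the arm. Let δ be the true treatment difference in change, and b a measurement shift affecting follow-up readings in one arm only. The expected difference in change is then δ + b. Baseline carries no information about b, so the baseline-adjusted MMRM estimates δ + b as well. Rank transformation does not separate the two either.

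**4. How sensitive is the test to b?** Inputs: δ = 0, 30 per arm with complete follow-up, two-sided 0.05, and SD 8 (planned) or 16 (the Section 9.2 SD of TcPO2 in this population). The values of b are assumptions; the documents give none.

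- Standard error = SD × √(2/30): 2.066 at SD 8, 4.131 at SD 16.
- Critical t on 58 degrees of freedom = 2.002. The smallest significant observed difference is therefore 2.002 × 2.066 = 4.1 mmHg at SD 8 and 2.002 × 4.131 = 8.3 mmHg at SD 16.
- Noncentrality = b / standard error. The rejection rate comes from the noncentral t distribution, both tails.

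| Assumed shift b (mmHg) | Noncentrality, SD 8 | False positives, SD 8 | Noncentrality, SD 16 | False positives, SD 16 |
|---|---|---|---|---|
| 0 | 0 | 5.0% | 0 | 5.0% |
| 1 | 0.48 | 7.6% | 0.24 | 5.7% |
| 2 | 0.97 | 15.9% | 0.48 | 7.6% |
| 3 | 1.45 | 29.8% | 0.73 | 11.0% |

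Only the ratio b/SD matters, which is why 1 mmHg at SD 8 and 2 mmHg at SD 16 agree. A shift of 2 mmHg is a quarter of the 8 mmHg target (2/8) and, at SD 8, about half the significance threshold (2/4.1).

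**The case against.** The open label is a declared choice in a small pilot, and no passage contradicts another. TcPO2 is an instrument reading with real safeguards. The bracketed 43-45°C reads as a tolerance around 44°C rather than a setting for the operator to choose, and recording the area used bears directly on electrode placement. Only follow-up readings can be affected. No document supports a shift of any particular size, and the calculation is an unadjusted t-test, whereas the plan is a baseline-adjusted MMRM. Wound, ABI, TBI and TSP assessments are routine care, whose staffing the trial may not control. Medical records are a data source, so leaving the arm off a request may not hide it.

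Most of this stands, and it limits the point. It does not remove it: a recorded area does not fix a point on a wound edge that may move as the wound heals, steady state has no numerical rule, and the safeguards say nothing about who knows the arm.

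A reader might go further and infer that a laboratory technician is already in place, so that masking costs nothing. The documents describe no such person; the only laboratory mentioned is the local one for blood tests. Nor do they say that wounds are judged by eye. The method is simply not stated.

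**Conclusion.** The point holds as a gap in the protocol. The month 3 and 6 TcPO2 and wound assessments have no masking provision, some operator judgement remains, and a post-randomization shift tied to the arm would pass straight into the primary estimate.

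The size is a sensitivity range: 7.6% to 29.8% false positives at SD 8 and 5.7% to 11.0% at SD 16, for assumed shifts of 1 to 3 mmHg. A reader might take the upper figure as the trial's expected error rate. It is not: it pairs the largest assumed shift with the smaller SD. Nor do the documents show that bias will occur, or that the operator does know the arm. They never say who operates the device. That knowledge is possible is an inference from the open-label design and the absence of any safeguard.

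**What to change.** Amend Sections 6.2 to 6.4 as follows.

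- **Order.** At months 3 and 6, take the TcPO2, SPP and study wound measurements before the compliance check, dispensing and adverse event questions.
- **Operator.** Where the current team has more than one member (Section 11.1 allows a nurse, coordinator or designee), have these measurements done by a member who has not been told the arm. Leave the arm off any request, and ask patients not to mention it.
- **Record.** Add an eCRF item stating whether the assessor knew the arm at each visit, with a sensitivity analysis by that item. With 30 patients per arm this can only be descriptive.
- **Scope.** Apply the same to the standard-of-care ABI, TBI and TSP only where feasible.

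The cost is protocol wording, one eCRF field, a fixed visit order and some accidental unblinding, which would be recorded. Drugs, sample size and primary analysis are unchanged, and no extra assessor is requested. The sponsor should confirm whether a separate operator is available. If one person does everything, visit order alone will not restore masking, because that person may know the arm from the first dispensing. The eCRF item would then at least document it.
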